9.2 Entinostat

9.2.1 Supply and Storage

Entinostat is a synthetic small molecule bearing the chemical name 3-Pyridylmethyl N-{4-[(2-aminophenyl)carbamoyl]benzyl}carbamate and the molecular formula C₂₁H₂₀N₄O₃, with a molecular weight of 376.41. Entinostat is classified as an antineoplastic agent, specifically functioning as an inhibitor of histone deacetylases that promotes hyperacetylation of nucleosomal histones, allowing transcriptional activation of a distinct set of genes that leads to the inhibition of cell proliferation, induction of terminal differentiation, and/or apoptosis.

Entinostat/placebo is an oral drug supplied by Syndax to the sites as pink to light red (1 mg) or yellow (5 mg) as polymorph B coated tablets. Each tablet contains mannitol, sodium starch glycolate, hydroxypropyl cellulose, potassium bicarbonate, and magnesium stearate as inert fillers. The film coating consists of hypromellose, talc, titanium dioxide, and ferric oxide pigments (red and yellow) as colorants.

Entinostat/placebo is to be stored at controlled room temperature (15°C to 25°C / 59°F to 77°F) in a secure, locked storage area to which access is limited.

Entinostat/placebo is to be protected from light. Entinostat/placebo is not to be exposed to extremes of temperature (greater than 30°C / 86°F or less than 5°C / 41°F). The pharmacist will dispense the investigational material to the patient at appropriate intervals throughout the study in childproof containers.

Entinostat/placebo will be supplied to patients in bottles containing enough pills for a 3-week cycle, plus an additional dose in case tablets are lost.

Please refer to the Pharmacy Manual for complete details regarding supply, storage accountability and destruction Entinostat.

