9.2.2 Dosing and Administration

All patients will self-administer entinostat/placebo PO once weekly on study days 1, 8 and 15 of each 21 day cycle. A new bottle of entinostat/placebo will be dispensed on day 1 of each cycle, regardless of the number of pills remaining in the bottle from the previous cycle.

On study days on which patients receive both entinostat/placebo and atezolizumab, entinostat/placebo is to be taken prior to atezolizumab.

Entinostat/placebo is to be taken on an empty stomach, at least 2 hours after a meal and at least 1 hour before the next meal.

If an entinostat/placebo dose is missed, it may be taken up to 48 hours after the scheduled dosing time. If it is not taken within the 48 hour window, the dose should not be taken and will be counted as a missed dose. The patient should take the next scheduled dose per protocol. Missed doses should be noted as such on the patient drug diary and in the eCRF.

If entinostat/placebo is vomited, dosing should not be re-administered but instead the dose should be skipped.

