9.5 Entinostat Compliance

Treatment compliance to entinostat will be assessed at the end of each cycle. Patients will complete a diary to document their weekly intakes. They will be instructed to return all unused drugs (partially used and empty containers) and their diary at each visit. Site staff will perform accountability of the returned drug and will assess patient compliance. Site staff must ensure that the patient clearly understands the directions for self-medication and follows the schedule.

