10.7 Extent of Exposure

Number of Cycles, Duration of Treatment, Cumulative Dose and Relative Dose Intensity (RDI) will be summarized by treatment for the safety analysis set.

Atezolizumab:

**Statistical Analysis Plan
SNDX-275-0602 (TRIO025)
DM-025-037**

- Number of Cycles: number of cycles having total dose > 0 mg reported
- Duration of Treatment (weeks) = [(Date of last dose - date of first dose) + 21] ÷ 7
- Cumulative Dose (mg) = sum of total dose administered as reported
- Weekly Dose Intensity (mg/week) = (Cumulative Dose) ÷ (Duration of Treatment)
- Planned Weekly Dose Intensity (mg/week) = 1200mg ÷ 3 weeks = 400
- RDI (%) = (Weekly Dose Intensity ÷ Planned Weekly Dose Intensity) × 100

Entinostat:

- Number of Cycles: number of cycles having total dose > 0 mg reported
- Duration of Treatment (weeks) = [(Date of last dose - date of first dose) + 21] ÷ 7
- Cumulative Dose (mg) = sum of total dose administered as reported
- Weekly Dose Intensity (mg/week) = (Cumulative Dose) ÷ (Duration of Treatment)
- Planned Weekly Dose Intensity (mg/week) = (Dose Cohort as assigned in Phase 1b or RP2D in Phase 2) ÷ 3 weeks
- RDI (%) = (Weekly Dose Intensity ÷ Planned Weekly Dose Intensity) × 100

The RDI will be additionally presented categorized (i.e., number and percentage of patients with RDI of < 60%, 60 - < 80%, 80 - < 90%, 90 - < 110%, ≥ 110%).

The number and percentage of patients with dose interruptions/discontinuations or reduced (entinostat/placebo at Phase 2 only), along with their respective reasons will be summarized.

For entinostat/placebo, the compliance will be summarized by visit using the following calculation:

$$\text{Compliance (\%)} = \frac{\text{Number of Tabs taken} + \text{Number of Tabs Returned}}{\text{Number of Tabs Dispensed}} \times 100$$

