11. LIST OF PLANNED TABLES, FIGURES, LISTINGS

11.1 Planned Tables

Title	Population	Description
Patient Disposition	FAS	Tabulates the disposition of all patients by treatment group, including the number of patients in each population set as well as the number of patients discontinued from study treatment, and the number of patients discontinued from study. The reason for drug discontinuation and study discontinuation will also be summarized.
Stratification Factors	FAS	Tabulates the stratification factor (Geographic Location – US vs. Rest of World) by treatment group. (Phase 2 only.)
Protocol Deviations	FAS	Tabulate the number of patients who reported protocol deviations by deviation category for each treatment group.
Eligibility Deviations	FAS	Tabulates the number of patients who violates inclusion/exclusion criteria by criterion for each

**Statistical Analysis Plan
SNDX-275-0602 (TRIO025)
DM-025-037**

Title	Population	Description
		treatment group
Baseline Demographics	FAS	Tabulates summary statistics of the demographics (age, race, ethnicity, menopausal status, weight, height and ECOG status at baseline).
Disease Characteristics	FAS and Safety	Tabulates summary statistics for time from initial diagnosis to randomization, primary tumor location, staging at initial diagnosis, histopathological type at initial diagnosis, histopathological grade at initial diagnosis, disease status at registration, time from metastatic/locally recurrent disease to randomization, hormonal receptor status, and HER2 status.
Prior Surgery for Breast Cancer	FAS	Tabulates the number of patients with type and location of surgery for each treatment group.
Prior Systemic Anti-Cancer Therapy	FAS	Tabulates the number of patients by type and indication of the systemic cancer therapy for each treatment group.
Prior Radiation Therapy	FAS	Tabulates the number of patients by site and indication of prior radiation therapy for each treatment group.
Medical History	FAS	Summarizes medical history by SOC and PT for each treatment group.
Study Drug Exposure	Safety	Summarizes the number of cycles, the duration of treatment, cumulative dose, and RDI by treatment group. The number of dose interruptions/discontinuation or reduction will also be summarized.
Compliance	Safety	Compliance assessment will be summarized by each visit.
Dose Limiting Toxicity	Safety	Tabulates the number of patients experienced DLT

**Statistical Analysis Plan
SNDX-275-0602 (TRIO025)
DM-025-037**

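### The SAP's entinostat/placebo compliance formula measures tablets accounted for, not doses taken, so skipped doses that are returned still score 100% (minor; one descriptive table)

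*SAP*

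**What the plan says.** SAP 10.7 (Extent of Exposure) introduces the measure with "For entinostat/placebo, the compliance will be summarized by visit using the following calculation". The numerator adds "Number of Tabs Returned" to the number taken, and the denominator is the number dispensed. SAP 11.1 commits to a Compliance table on the Safety set: "Compliance assessment will be summarized by each visit". The SAP gives no other definition of compliance.

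The protocol supplies the context:

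- Supply (9.2.1): "Entinostat/placebo will be supplied to patients in bottles containing enough pills for a 3-week cycle, plus an additional dose in case tablets are lost".
- Dosing (9.2.2): self-administered on days 1, 8 and 15 of each 21-day cycle, with missed doses entered in the diary and the eCRF. On dispensing: "A new bottle of entinostat/placebo will be dispensed on day 1 of each cycle".
- Returns (9.5): "They will be instructed to return all unused drugs (partially used and empty containers) and their diary at each visit".
- Timing (9.5): "Treatment compliance to entinostat will be assessed at the end of each cycle".
- Table 1-1 marks a compliance assessment at C1D1, C1D8, C1D15, C2D1, C2D15, day 1 of later cycles, the end-of-treatment visit and the safety follow-up visit.

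**The concern.** A compliance percentage should fall when a patient takes fewer doses than scheduled. This one need not. Returned tablets count in the patient's favour exactly as swallowed tablets do, and the schedule appears nowhere in the formula. A patient who skips doses and follows the return instruction looks perfect, while one who takes everything and loses the spare looks deficient, so the ratio can rank patients the wrong way round.

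Entinostat/placebo is self-administered and is the treatment that differs between the arms. A Compliance table close to 100% in both arms would be read as good adherence, when it would mainly show that bottles came back. The protocol keeps the two ideas apart: accountability has its own section (9.4), and 9.5 lists accounting for returned drug and assessing compliance as separate staff tasks.

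**Working it through.** The plan states no compliance result, so there is no figure to reproduce. The check evaluates the formula under the protocol's own supply and return rules.

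**Inputs, per 3-week cycle.** Let *k* be the number of tablets per dose.
- Scheduled: S = 3k (days 1, 8 and 15; Protocol 9.2.2).
- Dispensed: D = 4k (three doses plus one spare; Protocol 9.2.1).
- T = taken, R = returned, L = D − T − R = unaccounted for.

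**What the formula measures.** (T + R) ÷ D = (D − L) ÷ D = 1 − L ÷ D. It depends only on tablets that were neither taken nor returned.

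**Everything unused is returned (L = 0).**

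| Doses taken | Doses returned | SAP formula | Taken ÷ scheduled |
|---|---|---|---|
| 3 | 1 | 4k/4k = 100% | 3k/3k = 100% |
| 2 | 2 | 4k/4k = 100% | 2k/3k = 66.7% |
| 1 | 3 | 4k/4k = 100% | k/3k = 33.3% |
| 0 | 4 | 4k/4k = 100% | 0/3k = 0% |
| 4 (spare also taken) | 0 | 4k/4k = 100% | 4k/3k = 133.3% |

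The zero row is the algebraic limit. Because *k* cancels, the result holds for any number of tablets per dose.

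**Something is unaccounted for (taken counted from the diary).**

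| Pattern | SAP formula | Taken ÷ scheduled |
|---|---|---|
| 3 taken, spare lost | 3k/4k = 75% | 100% |
| 2 taken, skipped dose not returned, spare returned | (2k + k)/4k = 75% | 66.7% |
| 1 taken, 2 returned, 1 lost | (k + 2k)/4k = 75% | 33.3% |

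A score of 75% therefore fits full, two-thirds or one-third intake, and any of these intakes can also score 100%.

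**Timing.** The SAP summarises by visit. The protocol assesses at the end of each cycle and dispenses only on day 1 of a cycle. In cycles 1 and 2 there are visits with no dispensing (C1D8, C1D15, C2D15). At C2D1 the tablets coming back belong to the cycle 1 bottle while those handed out are for cycle 2. The SAP does not say which bottle supplies the denominator at a given visit. From cycle 3 there is one scheduled on-treatment visit per cycle, so the mid-cycle part of the mismatch is confined to the first two cycles.

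**The shortcut of deleting the returned term.** Taken ÷ dispensed gives a fully adherent patient 3k/4k = 75%, because the spare stays in the denominator.

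**The case against.** The strongest reply is that little depends on this table. Protocol 13.5.4 lists the exposure outputs as treatment duration, cycles, cumulative doses and dose modifications with reasons; a compliance statistic is not among them. Low intake also surfaces elsewhere:

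- SAP 10.7 summarises cumulative dose and interruptions, discontinuations and reductions with reasons, and SAP 11.2 lists exposure by visit.
- Missed doses are recorded in the diary and the eCRF.
- In Phase 1b, a patient without a DLT is DLT-evaluable only after receiving every Cycle 1 dose (Protocol 9.6).
- A footnote to the entinostat dose-modification tables ends study drug when more than half the doses in any 6 weeks are missed.
- Noncompliance is a listed reason for discontinuation (Protocol section 11).

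All of this stands, and it holds the severity at minor. It does not make the formula right: the SAP commits to a table labelled compliance whose number does not measure compliance.

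A second reply is that the source of the taken count is known. This also stands. A reader might infer that taken could be derived as dispensed minus returned, which would make the ratio 100% for everyone. The SAP names no source, but Protocol 9.4 and 9.5 give patients a diary in which to record intake, and nothing in either document describes the subtraction.

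**Conclusion.** The point holds, at minor severity. As written, the ratio is drug accountability. With unused tablets returned it is 100% at any intake, and with tablets missing it cannot separate a lost spare from a skipped dose. The 100% result rests on the return instruction being followed; the 75% results rest on a diary count of tablets taken. The by-visit presentation also needs reconciling with the end-of-cycle assessment.

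The effect stops at the descriptive Safety-set Compliance table. Three stronger readings are tempting and are not supported:

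- *That efficacy conclusions are affected.* PFS, alpha, power and the analysis sets do not use the ratio.
- *That an adherent patient would score 25% at C1D8 or 50% at C1D15* (one or two of four doses taken, counted before that day's dose). This requires tablets still in the bottle not to count as returned. Protocol 9.5 has partly used containers brought back at each visit, which gives 100%.
- *That this and the entinostat relative dose intensity form one defect.* The planned-intensity denominator in the same SAP section has its own problem and should be raised separately. It is not needed to establish this point.

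**What to change.** Replace the SAP 10.7 definition with a per-cycle one:

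Compliance (%) = 100 × tablets taken in the cycle (diary/eCRF) ÷ tablets scheduled in that cycle.

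Summarise it by cycle, and change the Compliance entry in SAP 11.1 to match. State whether recorded protocol-directed holds and reductions come out of the denominator. If they do, report a cycle with nothing scheduled as not applicable. State also whether a vomited dose counts as taken.

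Scoring by cycle is preferable to scoring between visits. Cycle 1 visit windows are ±1 day and a dose may be taken up to 48 hours late, so a permitted dose could fall into the wrong visit interval. A day-15 dose taken 48 hours late, on day 17, is still inside its 21-day cycle.

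Dispensed minus returned can serve as a cross-check but not as the measure, because it counts lost tablets as taken (spare lost: 4k/3k = 133%). Do not simply delete the returned term, for the reason shown in the working. If the present ratio is kept, label it drug accountability.

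The cost is low: one definition, one table program and, if holds and reductions are netted out, some programming to match them to cycles. Protocol 9.4 says return information is recorded at the site. That tablet counts reach the database is implied by the SAP formula but not stated, so confirm it first.

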10.8 Efficacy Analyses

Efficacy data for the primary endpoint and the secondary endpoints will be analyzed for the FAS and, where appropriate, the Per-protocol Set. Sensitivity analyses and subgroup analyses will be conducted as appropriate; refer to Table 2 and Table 3. Summaries and figures of the efficacy endpoints will be generated by treatment group as per randomization.

10.8.1 PFS

The duration of PFS will be summarized descriptively using Kaplan-Meier (KM) curves. Inferential comparisons between treatment arms will be made using stratified log-rank test, stratifying on

**Statistical Analysis Plan
SNDX-275-0602 (TRIO025)
DM-025-037**

geographic location (US vs. Rest of World). The KM estimate of the PFS survival distribution function will be computed for each treatment group using PROC LIFETEST with method=KM option in SAS. For each treatment group, the KM estimates for the median PFS time, the first and third quartiles will be presented, along with approximate 95% confidence intervals (CI) calculated using Greenwood's formula. Example of PROC LIFETEST code with and without stratification is presented below:

```
* Unstratified;
proc lifetest data=<PFS> method=km;
  time <pfsmmonth*<pfscens>(1);
  strata <trt>;
run;

* Stratified;
proc lifetest data=<PFS> method=km;
  time <pfsmmonth*<pfscens>(1);
  strata <geographical region> / group= <trt>;
run;
```

The effect of treatment on PFS will also be compared using a stratified Cox proportional hazards model. The hazard ratio with two-sided 95% CI will be derived from the stratified Cox proportional hazards model using PROC PHREG with ties=EXACT option in the model. Homogeneity in the hazard ratios between randomization strata will be examined by Wald's test. The corresponding results without stratification will be reported as supplemental analyses.

Example of PROC PHREG code with and without stratification is presented below:

```
* Unstratified;
proc phreg data=PFS;
class trt(ref='1');
model dfsmmonth*dfscens(1)=trt / risklimits ties=exact;
run;

* Stratified;
proc phreg data=PFS;
class trt(ref='1');
model dfsmmonth*dfscens(1)=trt / risklimits ties=exact;
strata <geographical region>;
run;
```

Testing of Proportional Hazard assumption will also be done using the following stratified model:

```
proc phreg data=pfs;
  model <pfsmmonths*<pfscens>(1)= <trt> / risklimits Ties=exact;
    assess var=(<trt>) ph / crpanel resample seed=199;
    strata <geographical region>;
run;
```

**Statistical Analysis Plan
SNDX-275-0602 (TRIO025)
DM-025-037**

In addition, Hazard Ratio for treatment effect will be estimated using a multivariate Cox proportional hazards model to be constructed by selecting variables among all the potential variables listed in the subgroup analysis (see Section 10.10) using stepwise selection method with entry p-value 0.05 and exit p-value 0.1. The treatment factor will be kept out of the model throughout the covariate selection process and only added into the final model. HR for treatment effect and corresponding 95% confidence interval (CI) will be estimated from the final model.

Note that a covariate may be removed from the analysis if the number of patients/events representing one level of that variable is insufficient or data collected on that variable are insufficient.

A sensitivity analysis will be performed to assess the impact of the different censoring mechanisms and deviations from the planned schedule of disease assessments; refer to Table 2.

